Methods: A Phase 2 clinical trial will be performed by a multi-center group of the NF Consortium, to compare treatment with or without INFUSE Bone Graft at the time of surgical repair. **Parents of patients will have the option of choosing whether they have a preference for the BMP group or the Control group. Those with a preference will be placed in the group of their choice (Choice Arm). Those without a preference will be placed in a Randomized arm, and will be randomized at a ratio of 3:2 for Control group:** **BMP group.** For all patients, a standard surgical procedure will be used, including: resection of pseudarthrosis tissue; placement of a rigid intramedullary rod; and placement of autogenous bone graft from iliac crest. For patients in the BMP group, the INFUSE device containing BMP-2 will in addition be applied intraoperatively to the osteotomy site. A minimum of 36 and maximum of 52 patients will be enrolled. Fracture union will be determined by scoring of radiographs (RUST score) for cortical bone fusion and callus formation at the osteotomy site. Score will be by a group of radiologists blinded to the group assignment of the patients. RUST score at 12 months post-surgery will be the **primary outcome measure** to determine efficacy. Secondary measures will include determination of time to healing (months); quality of life measures; functional walking measures; and incidence of refracture after surgery. This study, once successfully completed, will determine if use of INFUSE Bone Graft improves healing of tibial pseudarthrosis in NF1 and will document safety issues. Regardless of results, the better performing of the two groups (control or BMP) will be able to serve as a much-needed control arm for future studies of additional targeted therapeutic agents for NF1-related bone disease. An international working group of orthopaedic surgeons and NF specialists has been formed and is committed to successful completion of this trial.

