All patients will be immobilized for a minimum of 3 months after surgery in either a spica or above knee cast; surgeons will use clinical discretion to determine if further casting is needed on an individual basis. After the cast is removed, patients will be permanently braced (24 hours per day) in a custom-made above- or below-the-knee orthosis. **The primary outcome measure is radiographic evidence of union by the RUST scoring system at 12 months after surgery.** The rate of tibial healing will be assessed by application of the RUST scoring criteria for radiographs obtained at 6 weeks, 3 months, 6 months, 9 months, and 12 months after surgery. Quality of life will be assessed by the Pediatric Outcome Data Collection Instrument, and walking function will be assessed by the 10 meter timed walk, performed at baseline, 6 mos, and 12 mos. Biologic specimens including discarded pseudarthrosis tissue and bone fragments from the iliac crest will be collected at the time of surgery and sent to the Texas Scottish Rite Hospital.

The assessment of effectiveness of BMP-2 will be made by comparing the RUST union score at 12 months after surgery between the two groups (BMP-2 and Control). In addition, the rate of healing will be assessed by comparing the RUST score from radiographs at designated intervals in the post-operative period (6 weeks, 3 months, 6 months, and 12 months). Patients will continue to be followed in a registry with annual clinical assessments to determine long-term outcome, especially re-fracture and amputation.

Patients entered on the trial will be carefully monitored for the development of toxicities associated with BMP-2. BMP-2 and collagen antibody levels in serum will be measured preoperatively in all participants and results will be generated prior to enrollment for participants with documented prior exposure. All participants will be monitored at multiple intervals after surgery to test for antibody formation to the components of INFUSE.

Secondary Objectives:

Quality of life assessments for the 2 experimental groups will be obtained at baseline, and at 6 and 12 months after surgery. Pain assessment will be made at baseline and at clinical visits at 6 weeks, 3 mos, 6 mos, and 12 mos post-op). Functional walking outcome will be measured by the 10 meter walking test, performed at baseline, 6 and 12 months.

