5.5 FUNCTIONAL ASSESSMENT: Ten Meter Timed Walk

The **timed 10 meter walk test** is a functional outcome measure that has been used extensively in the fields of rehabilitation medicine, neurology, and orthopaedics. In this well-validated, easily administered test, a 10 meter (32.8 feet) hallway is measured and marked, with starting line and end line. The patient is given instructions either to walk the distance at his/her normal, comfortable speed, or as quickly as safely possible. The walk is timed using a standard stopwatch, and results are recorded in seconds. The patient performs the test 3 times, and the mean value of the 3 trials is used as the result. Results from this test will be compared for individuals at baseline, 6 mos after surgery, and 12 mos after surgery, and will be used as a secondary outcome measure. The timed 10 meter walk is easy to perform in a clinic setting without special equipment such as a gait analysis lab. The test has been used extensively in studies of muscular dystrophy, spinal cord injury and cerebral palsy, and has been validated from ages 4 years through adults [Pirpis et al, 2003]. It has also been used as an outcome measure in a Phase 3 clinical trial for multiple sclerosis [Cohen et al., 2001]. A 20% change in walking speed is considered to be significant. The test can be performed while a patient is in a brace or other adaptive device. This test and other functional outcome measures have recently been reviewed extensively by the REINS committee, and based on its reliability and ease of use was recommended as a secondary outcome measure for NF trials assessing ambulation.

The 10 meter Timed Walking Test will be performed before surgery, and at 6 months and 12 months post surgery. The test can be performed with the leg braced, and any bracing or other assistive device will be recorded at each time point. The test will be performed 3 times, and the mean of the 3 times (in seconds) will be recorded as the final score at each visit.

Data will be entered into eDES at the clinical sites and sent electronically to the DMAC for subsequent analysis.

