5.7 RISK/ BENEFIT ANALYSIS

Evaluation of benefits and risks/discomforts

The potential benefit from participation in this trial is improved union of surgically treated tibial pseudarthrosis, faster time to union, and improved quality of life. There are risks for surgery that exist regardless of enrollment on the clinical trial. The primary risks to the subjects from participation in this clinical trial are complications related to BMP-2. Toxicities and anticipated adverse events are outlined in Sections 2.1 and 2.2. Patients enrolled on this trial will be carefully monitored for the development of toxicities, including development of antibodies to BMP-2, and a toxicity stopping rule is in place to prevent additional patients from exposure to BMP-2. Clinical report forms, radiographic studies, and biologic specimens for future research studies, will have identifiers that can be traced to the patient only by contacting the NF Clinical Trials Consortium Operations Center. However, as the samples are linked to the patient's name, a small risk persists that unauthorized persons could gain access to information. Some testing may eventually reveal information that could result in discrimination with health or life insurance or employment. We believe that these risks are minimal since it is already known that patients enrolled on the study have NF1. All research results will be kept confidential.

Patients also have the right to withdraw the blood specimens obtained for research purposes at any time.

Potential benefits to all participants of this trial include: 1) receiving their surgery from an experienced surgeon with expressed interest in neurofibromatosis; 2) screening and treatment for factors such as low Vitamin D levels which may affect bone healing; 3) use of a standardized protocol for intramedullary rod and iliac crest bone graft; and 4) use of a standardized rehabilitation protocol. In addition, all participants will have Xray assessment of bone healing by a group of radiologists experienced in NF1 bone disease, using the RUST score, which may reflect a more accurate measure of bone healing than local radiographic reading.

Risk/benefit analysis

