All statistical analyses will be performed using SAS (version 9.3). All analyses are based on evaluable patients, as defined in section 10.5 with sensitivity analyses considering inevaluable patients as failures (scores 4-7). Summary statistics will be used to describe the study population (such as ranges, medians of ages, gender, baseline performance characteristics). The quality of life assessment in this study is based on the Pediatric Outcomes Data Collection Instrument, the PedsQL Pediatric Pain Questionnaire, and the 10 meter Timed Walk. From data collected on these questionnaires, scales are formed that measure domains such as global functioning, extremity and physical function, transfers and basic mobility, sports/physical function, happiness, and pain/comfort. These QOL and pain measures will be given pre-surgery, 3 months, 6 months, and 12 months after surgery. Since the scales are continuous, summary statistics will be generated for each measure at each time-point. The paired t-test will be used to look at changes in these measures from pre-treatment levels through 12 months. Longitudinal data analysis methods will be used to evaluate long-term changes in these measure using regression techniques employing mixed models.

In order to determine factors which may be prognostic for the success of BMP-2 treatment, we will perform Wilcoxon Rank Sum Tests to within each group to compare:

- 1) age \leq 8 years versus age $>$ 8 years
- 2) prior surgery versus no prior surgery; and
- 3) prior rhBMP-2 exposure versus rhBMP-2 naïve.

Regarding dose of rhBMP-2, those with 4.2 mg of rhBMP-2 implanted will be compared to those with 8.4 mg of rhBMP-2 implanted with respect to success rate using a chi square contingency table and with respect to number of adverse events using the Wilcoxon Rank Sum Test.

Relationships between quality of life measures and other variables (i.e., pain) will be investigated using correlational analyses. Performance status will be assessed using the Karnofsky Performance Scale. Generalized linear models will be used to evaluate changes in these scales and scores over time.

Early Stopping Rule

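### No BMP-versus-control contrast is stated for quality of life, pain or walking; the stated paired t-test measures change over time and cannot attribute it to BMP

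*Combined protocol and SAP*

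**What the plan says.** The Abstract (section 1.0) lists among the secondary measures "quality of life measures; functional walking measures; and incidence of refracture after surgery". Section 4.1 says "Quality of life assessments for the 2 experimental groups will be obtained at baseline", with repeats at 6 and 12 months. Section 5.7 names among the potential benefits of taking part "faster time to union, and improved quality of life".

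Section 6.2 (Analyses) defines the measures: "The quality of life assessment in this study is based on the Pediatric Outcomes Data Collection Instrument, the PedsQL Pediatric Pain Questionnaire", together with the 10 m timed walk. It then gives three methods:

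- A paired test of change since before surgery: "The paired t-test will be used to look at changes in these measures from pre-treatment levels through 12 months"
- A mixed-model regression of the same measures, described as being for change over the longer term
- A further class of model, given later in the same section: "Generalized linear models will be used to evaluate changes in these scales and scores over time"

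None of these mentions treatment arm. Section 5.5 describes the walk in the same way: "Results from this test will be compared for individuals at baseline, 6 mos after surgery, and 12 mos after surgery". The quality-of-life objective in section 2.3 is also worded as assessment at successive times.

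Other outcomes are treated differently. Sections 6.1 and 6.2 write a comparison between the two groups for the RUST score, successful outcome, time to union and study failures.

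**The concern.** The trial asks whether adding BMP to a standard operation helps. All children have the resection, rod, iliac-crest graft, cast and brace, so any change from before surgery mixes the effect of that common package, growth and recovery with any effect of BMP. A paired t-test asks whether the mean change differs from zero. It does not ask whether the change differs between arms.

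Two things are at stake. First, if the plan is followed as written, the secondary outcomes that matter most to families cannot answer the comparative question. Any between-arm model would have to be chosen after the data are seen. Second, if the paired test is run in each arm, readers will tend to compare the two p-values. With up to 26 BMP patients and possibly far fewer controls, the larger arm reaches significance more often for the same true change, and that could be read as benefit from BMP.

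**Working it through.** **Inputs from the documents.** BMP arm: at most 26 (section 4.2.2). Control arm: 10 to 26, with 26 ideal (section 4.2.2); minimum goal 15 (end of section 6.2). The documents give no expected change, SD, power or significance level for these outcomes.

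**The plan's own figure.** The only stated power is for RUST, and it serves here only to confirm the arm sizes. From the rates in section 6.2 (control 33/42/25%, BMP 15/20/65%):

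P(BMP better) + ½P(tie) = 0.33 × 0.85 + 0.42 × 0.65 + ½(0.33 × 0.15 + 0.42 × 0.20 + 0.25 × 0.65) = 0.5535 + 0.148 = 0.7015 (table: 0.702).

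A tie-corrected Wilcoxon test, one-sided 0.05, at 26 v 10 gives 65.6% power (stated 65%). The plan's arithmetic reproduces.

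**Paired test run by arm, no BMP effect.** Assumptions: two-sided 0.05; normally distributed changes; the same true mean change in both arms, equal to d SDs of the change score. In an arm of size n, the chance of significant improvement is P(T > t with 0.975 quantile, n−1 df), where T is noncentral t with noncentrality d√n. The arms are independent, so

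P(BMP only) = power(26) × [1 − power(control)].

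At d = 0.5, power is 0.688 for n = 26, 0.293 for n = 10 and 0.438 for n = 15:

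- 26 v 10: BMP only 0.688 × 0.707 = 49%; control only 0.293 × 0.312 = 9%.
- 26 v 15: BMP only 0.688 × 0.562 = 39%; control only 0.438 × 0.312 = 14%.
- 26 v 26: 0.688 × 0.312 = 21.5% in each direction.

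P(significant in BMP only), with no BMP effect:

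| Shared change (SD) | 26 v 10 | 26 v 15 | 26 v 26 |
|---|---|---|---|
| 0 | 2.4% | 2.4% | 2.4% |
| 0.3 | 27% | 25% | 21.5% |
| 0.5 | 49% | 39% | 21.5% |
| 0.7 | 46% | 27% | 7% |
| 1.0 | 20% | 5% | 0.2% |

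The row for no change is 0.025 × 0.975. The maxima are about 51% (10 controls, d about 0.58), 39% (15) and 25% (26). Simulation with 20,000 trials per setting agreed at 0.3, 0.5 and 0.7 SD (for example 49.1% at 26 v 10 and 38.5% at 26 v 15, both at 0.5 SD).

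**Paired test pooled over arms.** A BMP-only result cannot arise, but the result says nothing about BMP.

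**Between-arm test of change.** In the same simulations its false-positive rate was 4.7 to 5.4%. This assumes comparable arms. For a true arm difference of 0.5 SD at 26 v 10, the noncentrality is 0.5/√(1/26 + 1/10) = 1.34 on 34 df, which gives about 26% power. The difference detectable with 80% power is about 1.07 SD at 26 v 10 and about 0.79 SD at 26 v 26.

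**The case against.** **The plan does not say the test is run by arm.** This is correct. A reader might infer that section 6.2 prescribes within-arm tests that will often show benefit in BMP only. The documents do not support that. The t-test sentence is silent on arm, whereas the prognostic Wilcoxon tests in the next paragraph are explicitly placed within each group. The percentages above therefore apply only under the by-arm reading.

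**The mixed and generalized linear models could carry a treatment effect.** They could, but no arm or arm-by-visit term is named.

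**The objective and the walk test are worded as change over time, so the test fits them.** This is partly fair. But these are secondary measures of a trial designed to compare two groups, and other outcomes are given group comparisons.

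**Shared improvement is not assured.** This also stands. Children are braced full time and kept from sports for a year (section 5.2), and in the pilot survey 42% of first rod-and-graft operations did not give lasting union (section 3.7). With no change in either arm, the false pattern has a 2.4% chance.

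**The tilt toward BMP depends on imbalance.** At the ideal 26 v 26 there is none, and section 6.2 itself treats 10 controls as a worse scenario.

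**A between-arm test is not clean either.** Section 6.2 expects most data from the Choice Arm, where families select treatment and know it. The 5% error rate does not allow for that selection, or for reporting bias on parent- and self-reported scales.

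**Conclusion.** The concern holds as a gap in the specified analysis. The named test answers a different question from the trial's, the models give no treatment term, and no between-arm contrast for quality of life, pain or walking appears anywhere. This conclusion does not depend on whether the t-test is pooled or by arm.

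The numerical risk is conditional. It needs by-arm testing and a shared true change. A BMP-only rate above 20% requires a shared change of about 0.25 to 1.0 SD with 10 controls, 0.26 to 0.77 SD with 15, or 0.28 to 0.52 SD with 26. The shared change is an assumption that the documents cannot confirm. The tilt toward BMP arises only with unequal arms.

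The primary endpoint is unaffected. The change should be made, ideally before any outcome data are examined by arm.

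**What to change.** In section 6.2 (Analyses), name one between-arm estimate for each PODCI scale, the pain scale and the 10 m walk: the 12-month BMP-minus-control difference with its 95% CI. Take it from a mixed model with baseline value, arm, visit, arm-by-visit, age group (≤ 8 v > 8 years), prior surgery and Choice/Randomized cohort. Age group and prior surgery stratify only the Randomized arm (section 4.2.3), so in the combined analysis they are covariates. Label the paired changes as descriptive.

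Name the pain instrument that is actually collected. Section 6.2 cites the PedsQL pain questionnaire, whereas sections 5.4 and 5.8 and Appendix I schedule the Faces Pain Scale (Revised), completed from age 4. Align the visit list too: section 6.2 gives 3, 6 and 12 months for these measures, but PODCI and the walk are scheduled only at 6 and 12 months after baseline.

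The cost is SAP wording; no new visit or instrument is needed. Three limits should be stated:

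- Between-arm power is low, so the results should be reported as estimates with intervals and not as confirmatory tests across several scales.
- Faces pain data will be absent below age 4. The walk is described as validated from age 4, while entry is from age 2.
- A cohort term does not remove Choice Arm self-selection or unblinding, so parent- and self-reported results need cautious reading.

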Tibial pseudarthrosis is defined as a chronic non-union in a bone which has fractured. It can occur in the general population as well as in patients with NF1, although more than half of all individuals with TPA have NF1. In patients with NF1, TPA typically occurs in a bone which is congenitally dysplastic, presenting as an anterior-laterally bowed tibia and/or fibula which has a high risk for fracture. Stevenson et al. [1999] surveyed a multi-center cohort of patients with NF1 and tibial dysplasia and found that tibial dysplasia was 1) most often unilateral, 2) evident in the first year of life, and 3) affected males more often than females by a ~2:1 ratio. Additional findings demonstrated that tibial pseudarthrosis usually results as a progression from tibial anterolateral bowing. This anterolateral bowing is recognized as **tibial dysplasia**, whereas the non-union of bone after fracture is defined as **tibial pseudarthrosis** (Figure 1). Analyses in the report by Stevenson et al. [1999], which reviewed a total of 160 NF1 subjects, showed that 61-66% of individuals with tibial dysplasia progressed to fracture and pseudarthrosis. The average age of fracture was 4.6 years with a range of 0 to 28 years, and the average number of surgeries in cases with pseudarthrosis was 3, with some patients having as many as 10 surgical procedures.

Figure 1 A and B: Radiographs of tibial dysplasia

TPA in NF1 patients leads to major morbidity, including possible lower leg amputation. Presently, best care guidelines for the treatment of TPA in NF1 do not include medical management protocols. We have assembled a multidisciplinary team of clinicians who provide specialized care for patients with NF1. Principal investigators of this clinical trial participated in two clinical trial strategy meetings for treatment of bone abnormalities in NF1 (New York City, 02/2008 and 4/2011) [Elefteriou et al., 2009], which led to a consensus to prioritize the development of a clinical trial for the combined medical/surgical treatment of tibial pseudarthrosis (TPA). Drs. [name], [name], and [name] recruited [name] to jointly work with the NF Clinical Trials Consortium to develop a multi-center clinical trial that implements medical treatment combined with well-established surgical protocols to optimally manage tibial pseudarthrosis in NF1 patients.

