Subjects of both genders, from all racial and ethnic groups are eligible for this trial if they meet the criteria outlined in Section 4.3. To date, there is no information that suggests differences in drug metabolism or disease response among racial or ethnic groups or between the genders, indicating that results of the trial will be applicable to all groups. Most tibial pseudarthrosis arises in early childhood, with fewer cases after age 11, thus we anticipate an enrollment of younger children. If differences in outcome that correlate to gender, age, racial, or ethnic identity are noted, accrual may be expanded or additional studies may be performed to investigate those differences.

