4.2.3 Enrollment procedures

The NF Clinical Trials Consortium will enroll subjects in this trial. Selected subjects with NF1 and tibial pseudarthrosis will be enrolled at the participating sites where surgery is anticipated. Personnel at the UAB NF Clinical Trials Consortium Operations Center will coordinate enrollment with the participating site, and ensure that eligibility requirements are met, prior to scheduling of surgery and shipment of rhBMP-2. As part of the consent process, patients and families will be provided information about the research aspect of this prospective clinical trial.

Study Modification: Enrollment: Patients may be enrolled on the study once all eligibility requirements for the study have been met. All patients/parents will discuss the study in detail with their surgeon, and will view a Powerpoint presentation about the study with a study coordinator present. **At the time of enrollment, parents/patients will be offered to choose either the Choice Arm or Randomized Arm of the study.** Those selecting the Choice Arm will be assigned to their treatment of choice (either BMP or Control). Those who choose the Randomized arm will be randomly assigned at a 2:3 ratio to BMP or Control group. It is

expected based on prior experience that more patients are likely to prefer the BMP arm. Therefore, the mildly unequal randomization of 2 BMP: 3 Controls is planned to improve the ability to achieve adequate controls for the study. For those in the Randomized arm, assignment will be accomplished by accessing a password controlled website maintained by the DMAC. The website is 21 CFR 11.10(d) compliant for FDA clinical trials.

That website will assign a new subject to a treatment group determined by a randomization list produced by the study statisticians employing a permuted block design. Randomization will be stratified by age (≤ 8 vs > 8 years) and prior surgery (Y/N). Enrollment and randomized treatment assignment must occur before the date of surgery but should be as close to the date of surgery as feasible.

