4.2.4 Informed Consent/Accent

The investigational nature and objectives of the trial, the procedures and treatments involved and their attendant risks and discomforts, and potential alternative therapies will be carefully explained to the patient or the patient's parent(s) or guardian if the patient is a child, and a signed informed consent and assent will be obtained according to both institutional and U.S. Army Medical Research and Materiel Command, Office of Research Protections, Human Research Protection Office (USAMRMC ORP HRPO) guidelines. Patients between the ages of 2 – 18 years at time of surgery will be eligible for consent. The principal investigator at the enrolling site will be responsible for obtaining informed consent. The study trial coordinator can provide information on the study and obtain consent if qualified as determined by the PI of the site. Most patients in this study will be less than 7 years of age. Those older than 7 will undergo age-appropriate assent tailored for both children aged 7-12 years, and for those aged 13-17 years (or until the age of majority in the state of the clinical center).

A study participant should sign the institution's HIPAA Consent.

A study participant should sign the institution's Release of Medical Information Waiver.

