4.3 PATIENT ELIGIBILITY/ INCLUSION AND EXCLUSION CRITERIA

Any individual with NF1 based on either NIH-diagnostic criteria or congenital pseudarthrosis of the tibia plus documented mutation in the *Nf1* gene is eligible for this study. Furthermore, decisions for surgical intervention must be made on a clinical basis with a determination that intramedullary rod plus autogenous bone graft is the most appropriate management approach for that individual patient. Patients may be enrolled only at the time of 1st or 2nd surgery for tibial pseudarthrosis, not subsequent surgeries. Candidates must be able to travel to an orthopedic surgical site that is participating in the study. Patient insurance must approve coverage of the surgical procedure and short-term post-operative care at the orthopedic center performing the operation, or patients can use a self-pay procedure to cover the surgical and hospital costs associated with the surgical procedure.

Inclusion Criteria for all patients:

- All patients who do not have a documented *NF1* mutation must meet the clinical diagnosis of NF1 using the NIH Consensus Conference criteria. In addition to tibial pseudarthrosis, one or more of the following diagnostic criteria for NF1 must be present:
 - Six or more café-au-lait spots ($\geq 0.5\text{cm}$ prepubertal; $\geq 1.5\text{cm}$ postpubertal)
 - Freckling in the axilla or groin
 - Optic pathway glioma
 - Two or more iris Lisch nodules
 - Two or more neurofibromas or one plexiform neurofibroma
 - A first-degree relative with NF1
- Patients must have tibial pseudarthrosis that has the potential to cause significant morbidity. Radiographic findings (AP & lateral leg radiographs) must support the diagnosis of tibial pseudarthrosis with chronic non-union.
- Age between 2 years and 18 years of age at time of study entry.
- Performance Level: Karnofsky $\geq 50\%$ for patients > 10 years of age and Lansky ≥ 50 for patients ≤ 10 years of age (Appendix III).
- Prior Therapy:
 - Patients who have undergone 1 previous surgery for tibial pseudarthrosis repair will be eligible to enter the study if they have refracture. Use of BMP-2 in the prior surgery is permitted, however patients with prior exposure must be screened for antibodies to BMP-2, bovine collagen, and rhBMP-2 neutralizing antibodies.

- Prior use of BMP-2 is allowed but will be recorded as a possible compounding factor.
- Patients who have had 2 or more prior surgeries for pseudarthrosis repair are ineligible

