As noted above we are likely giving up some power with this change to a Choice Design. Our assumption based on the current rate of declining to participate is that more patients will chose the BMP arm above the Control arm, but if we are incorrect, we would have adequate power (76% - 82%) if we were able to enroll 15-20 patients in the Control arm and 26 patients in the BMP arm. Even in a worse scenario that we were only able to recruit 10 patients to the Control arm + 26 to BMP, we would still have reasonable power of 65% to show a difference between the groups.

It is important to note that, although participants and providers in the Choice Arm will no longer be blinded to the treatment status of the participants, the Primary Outcome Measure (RUST score), will be determined by a group of 4 radiologists, all blinded to the treatment status of all participants.

Missing data: Reason for any missing 12 month radiographic data will be recorded by treatment group. Data from subjects missing the 12 month radiograph will not be included, unless multiple imputation is applied. Although minimal data are expected to be missing, multiple imputation technique will be used if 5% or more data are missing. This multiple imputation will replace the missing value with a set of plausible values that represent the uncertainty about the right value to impute. The multiply imputed data sets will then be analyzed by using the Wilcoxon Rank Sum Test for complete data on each and combining the results from these analyses. The variables used for the imputation will be RUST score at 6 months, age, prior surgery (Yes=1, No=0), and timed 10 meter walk at 12 months post-surgery.

Generalizability of the Results:

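### Age as a prognostic factor is tested only as 8 or under versus over 8 years; age in years would use more of the data already collected

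*Combined protocol and SAP*

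**What the plan says.** To find prognostic factors, section 6.2 (Analyses) states "we will perform Wilcoxon Rank Sum Tests to within each group to compare" three pairs of subgroups. The first is age of at most "8 years versus age $>$ 8 years". The sentence names neither the outcome (presumably 12-month RUST) nor a significance level, and gives no power or expected counts.

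On the ages to be expected:

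- Section 4.3 admits children by "Age between 2 years and 18 years of age at time of study entry".
- Section 4.2.4 says "Most patients in this study will be less than 7 years of age".
- Section 4.2.1 (Subject Accrual) says "Most tibial pseudarthrosis arises in early childhood, with fewer cases after age 11, thus we anticipate an enrollment of younger children".
- Section 3.1 reports, for a cited series, "The average age of fracture was 4.6 years with a range of 0 to 28 years".

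Age appears in three other places, none of which tests it. Section 4.2.3 says "Randomization will be stratified by age (≤ 8 vs > 8 years) and prior surgery (Y/N"), which applies to the Randomized arm. Section 6.2 lists age among the imputation variables, without saying in what form. It also plans descriptive summaries of age, so each child's age will be held. No reason is given for a cut at 8 years.

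**The concern.** A two-way split treats a child of 2 and a child of 8 as the same, and likewise a child of 9 and one of 18. With most children expected to be under 7, one side of the split is likely to be small, and in a small control group it may be empty. If healing changes steadily with age, the test has less chance of showing it than an analysis that uses each child's age.

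The stakes are modest. The analysis is exploratory. The plan does say, however, in sections 4.2.1 and 6.0, that an age-related difference in outcome may lead to wider enrolment or further studies. An insensitive test is a poor basis for that judgement, and a non-significant result from it would tell the reader little about age.

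**Working it through.** **Inputs from the documents.** BMP group: at most 26. Controls: 10 to 26 (section 4.2.2), with a minimum goal of 15 stated at the end of section 6.2. RUST bands 4–7 / 8–9 / 10–12: controls 33/42/25%, BMP 15/20/65% (section 6.2).

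**Inputs assumed.** The documents give no age distribution. Ages were taken as log-normal, truncated to 2–18 years, with median 4.6 to 6.5 and log-SD 0.5. This puts 57–79% under 7 and 14–33% over 8, in keeping with most being under 7.

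**1. The plan's own figure.** There is none for the age test, so the method was checked on the primary comparison. The probability that a BMP patient scores better, counting ties as half, is 0.33 × (0.20 + 0.65) + 0.42 × 0.65 + ½ × (0.33 × 0.15 + 0.42 × 0.20 + 0.25 × 0.65) = 0.5535 + 0.148 = 0.7015. This agrees with the 0.702 in the power table. The rank-sum power for ordered categories is then 86.4% for 25 v 25 (stated: 86%) and 66.1% for 26 v 10 (stated: 65%). All table entries agree within 1.3 points.

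**2. Expected size of the older group.** BMP: 0.14 × 26 = 3.6 to 0.33 × 26 = 8.6, so about 4 to 8 children (9 if the top is rounded up). Ten controls: 1.4 to 3.3, so about 1 to 3. The text alone bounds the older share only at under half: at most 12 of 26 and 4 of 10, if that holds in each group.

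**3. What the split can detect.** Suppose older and younger children differed by as much as the hypothesised BMP effect (0.70). The same formula gives one-sided power of 36–57% with 3–8 older children among 26, and 17–28% with 1–3 among 10.

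**4. The extreme cases.** With one older child among 10, the smallest exact p-value is 1/10 = 0.10 one-sided, or 0.20 two-sided. With none, the test cannot be run. If 16% are over 8, the chance of none is 0.84^10 = 0.17 with 10 controls, 0.84^15 = 0.07 with 15 and 0.84^26 = 0.01 with 26.

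**5. Split against age in years, steady trend.** Simulation with the RUST bands above, an assumed log-odds of 1 per SD of age in either direction, and two-sided 5%; Wilcoxon at 8 years against Spearman correlation with age:

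| Group | Split at 8 | Age in years |
|---|---|---|
| BMP, n = 26 | 8–49% | 42–59% |
| Controls, n = 10 | 5–11% | 22–30% |
| Controls, n = 26 | 28–46% | 57–68% |

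A separate run with the effect set per SD of log age gave 4–38% v 47–53% (BMP), 3–13% v 22–25% (10 controls), 10–23% v 34–37% (15 controls) and 23–40% v 58–61% (26 controls). The figures are therefore rough. The ranges cover several age distributions and both directions of effect, which is why the BMP ranges in the table overlap. Within each single scenario, age in years had the higher power.

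**6. A weaker trend.** At log-odds 0.5 per SD of log age, power was 3–17% v 20–23% (BMP) and about 3% v 10–12% (10 controls).

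**7. A step at 8 years.** If older children heal worse from 8 years on, with no trend otherwise, the order reverses in the BMP group: about 50–59% with the split and 27–42% with age in years.

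**The case against.** The strongest case for the plan is that the cut is pre-specified, equals a randomisation stratum, and serves an exploratory question for which no error rate or power is claimed. That stands, and it is a reason to keep reporting the split. It is not a reason to report only the split. The stratum governs only the Randomized arm, while section 6.2 expects most data to come from the Choice arm.

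A real threshold near 8 years would favour the split. This also stands: the documents do not establish the shape of the age effect, and step 7 shows the cost of guessing wrong. Nor does age in years rescue a 10-patient control group, where power stays low either way.

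The age inputs are softer than they look. The 4.6 years is age at fracture in a cited series, not age at entry. Entry requires age 2 or over and chronic non-union, and admits a second surgery after refracture, all of which push ages upward. Most being under 7 means only more than half. That the older group is very small is therefore an inference.

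Three stronger readings are tempting and are not supported:

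- *Nearly all the variation in age lies at 8 or under.* With the skewed ages assumed here, only 15–31% of the variance of age in years (about 32–53% on the log scale) lies within that group. About 60–67% of the variance in years lies between the two groups, because the older tail carries much of it.
- *The split keeps only 34–58% of the information in age.* That follows from the normal-covariate formula φ(z)²/(p(1−p)) with 10–30% over 8. It should not be applied to skewed ages.
- *A null result will be reported as showing that age does not matter.* The plan does not say so.

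**Conclusion.** The point holds as a low-cost improvement to an exploratory analysis. The plan's only test of age is a split at 8 years within each group, although most children are expected to be under 7 and exact age is collected. For a steady trend the split has clearly less power than age in years. In the BMP group of 26 the figures are roughly 8–49% against 42–59%, and the disadvantage holds at every control-group size examined.

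The figures rest on an assumed 14–33% over 8 and an assumed log-odds of 1 per SD. The order of the two methods rests on a trend that is steady rather than a step at 8. The risk that the test cannot be run at all is material only in the smallest control group: about 17% with 10 controls and 7% with 15, if 16% are over 8. The primary comparison and the stopping rules are not affected.

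**What to change.** In section 6.2 (Analyses), reword item 1 so that the main age analysis is the association between age in years and 12-month RUST, with a confidence interval. Either a Spearman correlation within each group or age in years in a proportional-odds model would do. Keep the 8-year Wilcoxon comparison as a secondary result that matches the randomisation stratum, and report the number of children in each cell. State that it will be omitted where a cell is empty.

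The cost is about one line of wording and no new data. The downside is that a monotone trend is assumed. Keeping the split covers the case of a step at 8 years. With about 10 controls, the confidence interval should be read in place of the p-value, since neither analysis has much power there.
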